8.1.2 DEFINITION OF SERIOUS ADVERSE EVENTS (SAE)

The following definition is used:

Serious Adverse Event (SAE): Adverse event that:

- a) led to a death,
- b) led to a serious deterioration in health of the subject, that either resulted in: a life-threatening illness or injury, or a permanent impairment of a body structure or a body function, or in-patient hospitalization or prolongation of existing hospitalization,

Early BIRD Version 9.0
Protocol 4039 27 JAN2019

or — in medical or surgical intervention to prevent life threatening illness or — injury or permanent impairment to a body structure or a body function.

c) led to foetal distress, foetal death or a congenital abnormality or birth defect.

Note: Planned hospitalization for a pre-existing condition or a procedure required by the protocol (e.g., the index implant procedure), without serious deterioration in health, is not considered a serious adverse event.

8.1.3 ADVERSE DEVICE EFFECT (ADE)

The following definition is used:

Adverse Device Effect (ADE): An adverse event that is related to the use of an investigational medical device.

This definition includes adverse events resulting from insufficient or inadequate instructions for use, deployment, implantation, installation, or operation, or any malfunction of the investigational medical device. This definition also includes any event resulting from use error or from intentional misuse of the investigational medical device.

8.1.4 SERIOUS ADVERSE DEVICE EFFECT (SADE)

Adverse device effect that has resulted in any of the consequences characteristic of a serious adverse event.

8.1.5 UNANTICIPATED SERIOUS ADVERSE DEVICE EFFECT (USADE)

The following definition is used:

Unanticipated Serious Adverse Device Effect (USADE): A serious adverse device effect which by its nature, incidence, severity or outcome has not been identified in the current version of the risk analysis report.

NOTE: Anticipated SADE (ASADE): an effect which by its nature, incidence, severity or outcome has been previously identified in the risk analysis report.

8.1.6 PRE-SPECIFIED LIST OF ADVERSE EVENTS

Adverse events listed below are provided on the case report form along with a method for recording other adverse events not listed, based on the recognized standard ANSI Z80.27-2014.⁷

- Corneal edema
- Progression of cataract requiring cataract extraction

- Wound leak
- Suture abscess or other local infection
- Endophthalmitis
- Chronic iritis
- Hyphema
- Strabismus
- Macular edema
- Vitreous hemorrhage
- Suprachoroidal hemorrhage
- Retinal detachment
- Device malfunction
- Device blockage not requiring surgical revision
- Device blockage requiring surgical revision
- Implant migration (of any kind) not requiring surgical intervention
- Implant migration requiring surgical revision
- Implant exposure or extrusion
- Flat anterior chamber requiring anterior chamber reformation
- Hypotony (e.g., IOP <6 mmHG and associated with concomitant hypotonous findings are noted, including: Corneal edema/folds, shallow anterior chamber, hypotonous maculopathy, significant choroidal detachments or effusion)
- Hypotony maculopathy
- Choroidal effusion requiring surgical drainage
- Substantial increase in IOP vs. baseline (defined as >10 mmHg)
- Substantial visual field loss vs. baseline (e.g., 10 db loss)
- Substantial visual acuity loss vs. baseline (e.g. 10 or more ETDRS letters)
- Event requiring unplanned ocular surgical re-intervention

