2.3 POTENTIAL RISKS AND BENEFITS

2.3.1 KNOWN POTENTIAL RISKS

Known **potential risks of** the BGI and the associated implant procedure may include:

- Adverse Result to Patient
- Aborted Procedure
- Bleeding
- Cataract formation or progression
- Choroidal detachment
- Choroidal effusion requiring surgical drainage
- Channel blockage
- Chronic iritis
- Corneal Haze/Opacity
- Corneal false tract above Descemet's membrane
- Corneal Neovascularization
- · Conjunctival overgrowth
- Corneal endothelial touch
- Death
- Delayed Procedure
- Deposits on device
- Device malfunction
- Device Migration or Dislodgement
- Device Rejection
- Endophthalmitis
- Flat anterior chamber requiring anterior chamber reformation
- Focal conjunctival hyperplasia
- Infection

- Inflammation including iris, macular and corneal edema
- Hematoma or Hemorrhage including suprachoroidal or vitreous hemorrhage
- Hyphema
- Hypotony (IOP < 6 mmHg when conscious)
- Hypotony maculopathy
- Increased tearing
- Ocular Trauma
- Peripheral flow/ wound leak
- Permanent Loss of Vision
- Phthisis / atrophy (shrinkage of the eye)
- Ptosis
- Pyrogenic
- Re-intervention
- Retinal Detachment
- Secondary surgical interventions
- Substantial increase in IOP vs. baseline
- Severe Irritation including Chronic Iritis
- Temporary Hypotony associated with General Anesthesia
- Temporary Loss of Vision
- Toxicity
- User Dissatisfaction
- Retrograde flow and increased IOP with swimming/diving

There may also be other risks related to the BGI and associated implant procedure that are not listed or that are not known at this time. This study will help characterize the adverse events associated with the BGI implant.

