- 29. Investigators can refer to infectious specialists or other ophthalmic specialists such as retinal surgeons, if needed.
- 30. The protocol includes assessment for signs of TASS, including symptoms of severe anterior chamber inflammation within 12-48 hours' post-operative period indicated by:
 - a. Corneal edema extending from limbus to limbus.
 - b. Dilated or irregular pupil.
 - c. Increased intraocular pressure.
 - d. Hypopyon.
- 31. Subjects will be examined for signs of ocular pathology at each scheduled follow-up visit.

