2.3.4 SUMMARY OF BENEFIT VERSUS RISK

Given the design and intended use of the device, infection and hypotony are perhaps the most serious risks posed. Extensive bench and animal studies (greater than 50 implants) suggest that design features of the device, particularly the highly hydrophilic hydrogel construct of the inner flow channel, are effective in resisting infection – with no clinical evidence of any infection, confirmed by negative culture. No cases of hypotony have been observed, even in the presence of multiple implants in a single eye.

Device dislodgments have been observed with earlier versions of the device. In all cases of dislodgment, the wound spontaneously healed with no clinical sequelae – including infection. Also in all cases, dislodgements were preceded by visual signs of conjunctival hyperplasia and peripheral leakage of aqueous humor around the device. With respect to dislodgments, it is important to note that the incision made at implant is less than half the size of those made during cataract surgery, and those are done without suturing after the procedure. The BGI – flat, at just 150 microns thick - is placed through the small incision, filling the incisional space. Upon dislodgment, the original incision has spontaneously closed - just as in the case with the larger incisions made during cataract surgery.

The intended patient population for this feasibility study are patients with elevated IOP but who have lost useful vision. These patients may be on medicated eyedrops that can cause pain, irritation, and discomfort on the eye. Finally, some of these patients may even experience pain resulting from excessive IOP, despite medications and other pressure-reducing therapies.

The BGI has the potential to reduce intra-ocular pressure in these patients, relieving pressure-associated pain and sparing whatever vision may be left. The BGI will also provide lubrication to the surface of the eye, relieving pain and irritation associated with medicated eye drops or other form of ocular surface disease. While implantation of a BGI is associated with risks (e.g. infection, hypotony, dislodgment, etc.), the potential benefit of BGI implantation should offset those risks in this patient population, particularly considering useful vision has already been lost.

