7.1.3.2 APPLANATION TONOMETRY

Intraocular pressures (IOPs) of the test and control eyes are measured with a Goldman Applanator according to the Goldman method. Two measures are taken from each eye and the average is calculated. Diurnal IOPs may be collected, as described above, for three measurements taken four hours apart, and recorded in a 24 hour clock format.

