7.2.5 SCHEDULE OF EVENTS TABLE

Table 3 Schedule of Events

Procedures	Screening/Baseline	Implant	Day 1	Week 1	Week 2	Month 1	Month 2	Month 3	Month 6, 12 & 24	Month 4.5, 8, 10, 15, 18, &21	Unscheduled
Informed Consent	Χ										
Eligibility Verification	Χ										
Medical History (including physical exam)	Х										
BGI Implant		X									
Best Corrected Visual Acuity (ETDRS)	Χ			X	Χ	Χ	Χ	X	Χ		Χ
Applanation Tonometry	Χ		Χ	X	Χ	Χ	Χ	X	Χ	Χ	Χ
Diurnal IOP	Χ								Χ		
Body Temperature	Χ		Χ	X	Χ	Χ	X	X	X		Χ
Central Corneal Thickness	Χ								X		
Slit Lamp Examination	Χ		Χ	X	Χ	Χ	Χ	X	Χ		Χ
Vertical C/D Ratio	Χ								Χ		
Corneal Surface Stain	Χ								Χ		
Indirect Ophthalmic Examination/Dilated Fundus Exam	X				Χ	Χ	X	Χ	X		X
Corneal Endothelial Cell Count	Χ							X	Χ		
Gonioscopy	Χ							X	X		
Optic Nerve Image Analysis	Х								X		
Perimetry of non implanted eye	Х								Х		
Seidel's Test		X	Χ	Χ	Χ	Χ	Χ	Χ	Χ	Χ	Χ
Schirmer Tear Test	Х					Χ		Χ	Х		
Lens Status for Phakic Eyes	Х					Χ		Χ	Χ		
Treatment Satisfaction Questionnaire	Х					Х		Х	Χ		
CIGTS	Χ					Χ		Χ	Χ		
Implant Site Photograph		X	Χ	Χ	Χ	Χ	Χ	Χ	Х	Х	Χ
Screening CRF	Х										
Implant CRF		Х									
Day 1 CRF			Χ								
Week 1 CRF				Χ							
Week 2/Month 2/Unscheduled CRF					Χ		Χ				Х
Month 1/Month 3 CRF						Χ		Χ			
Month 6/Month 12/Month 24 CRF									Χ		

Procedures	Screening/Baseline	Implant	Day 1	Week 1	Week 2	Month 1	Month 2	Month 3	Month 6, 12 & 24	Month 4.5, 8, 10, 15, 18, 821	Unscheduled
Month 4.5, 8, 10, 15, 18, and 21 CRD										X	
Adverse events		X	X	Χ	X	Χ	X	X	Χ	Χ	X
Medication Log	Χ	Χ	Χ	Χ	Χ	Χ	X	X	X	X	X
Device Experience CRF (if applicable)		Χ	Χ	Χ	Χ	Χ	Χ	X	X	X	X
Explantation CRF (if performed)		Χ	Χ	Χ	Χ	Χ	X	X	Χ	X	X
End of Study CRF (when conducted)		Х	Χ	Χ	Χ	Χ	X	X	Χ	X	X

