8.1.1 DEFINITION OF ADVERSE EVENTS (AE)

The following definition is used:

Adverse Event (AE): Any untoward medical occurrence, unintended disease or injury or any untoward clinical signs (including an abnormal laboratory finding) in subjects, users or other persons whether or not related to the investigational medical device.

- NOTE 1: This definition includes events related to the investigational device or the comparator.
- NOTE 2: This definition includes events related to the procedures involved.
- NOTE 3: For users or other persons, this definition is restricted to events related to investigation medical devices.

If an adverse event leads to multiple outcomes that sequentially worsen, only the worst adverse event is reported. For example, abnormal healing leading to infection would be reported as a single AE for the infection.

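### The listed hypotony adverse event requires clinical findings as well as IOP below 6 mmHg, and no low-IOP rate is prespecified, so low pressures without findings need not reach the primary safety table

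*Protocol*

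**What the plan says.** Protocol 2.3.4 states that "infection and hypotony are perhaps the most serious risks posed". The risk list in Protocol 2.3.1 gives a purely numeric meaning: "Hypotony (IOP < 6 mmHg when conscious". The adverse event list in Protocol 8.1.6 words the term as "Hypotony (e.g., IOP <6 mmHG and associated with concomitant hypotonous findings are noted", and goes on to name corneal edema or folds, a shallow chamber, maculopathy, and significant choroidal detachment or effusion. The same list treats raised pressure by number alone: "Substantial increase in IOP vs. baseline (defined as >10 mmHg".

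Two passages of management guidance also use low-pressure thresholds. Protocol 7.3.5 advises considering less IOP-lowering medication below 6 mmHg, with no findings required. Protocol 7.3.2 refers to IOP below 5 mmHg at more than 2 visits together with findings.

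SAP 4.1 makes the primary safety summary a table of reported adverse events by type through 6 months, giving events, participants and percentage of N. The SAP does not mention hypotony. Its only absolute IOP cut-off is a diurnal value of 14 mmHg or less (SAP 3.2).

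**The concern.** For a shunt that drains to the eye surface, pressure that falls too low is a central safety question. A reader will look for it first in the SAP 4.1 table. If that table shows no hypotony, the reader cannot tell whether every eye stayed at 6 mmHg or above, or whether some eyes fell below it without a documented finding. Both outcomes fit the listed term.

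Efficacy has the opposite asymmetry. A very low diurnal pressure at Month 6 meets both responder definitions and can be counted as benefit while the primary safety table says nothing about it. Protocol 10.5 expects ten subjects to suffice to confirm preclinical findings, and one of those findings (Protocol 2.3.4) is that no hypotony was observed. SAP section 1 says that the analyses support a future IDE submission, so the hypotony rate will be relied on.

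**Working it through.** The plan states no hypotony rate, so there is no figure to reproduce. The check compares definitions, outputs and the visit schedule, and then sizes one eye.

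**1. Where a reading below 6 mmHg without findings would go**

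| Place | Does it count? |
|---|---|
| Protocol 2.3.1, risk definition | Yes |
| Protocol 8.1.6, listed adverse event | Not by the wording of the term; may be reported at the investigator's judgement |
| Protocol 10.4.2, second analysis | Only if hypotony causes injury or needs invasive intervention |
| SAP 4.1, primary safety table | Only if reported as an adverse event |
| SAP 3.1 and 3.2, responder definitions | Counts as a response if it is the Month 6 diurnal value |

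**2. Efficacy with no floor**

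Inclusion requires IOP of 21 to 50 mmHg. I assume that the diurnal baseline lies in the same range.

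- The 20% criterion from a baseline of 21 is met at 21 × 0.80 = 16.8 mmHg or less.
- A fall from 21 to 6 mmHg is (21 − 6)/21 = 71% reduction. From 50 to 6 mmHg it is (50 − 6)/50 = 88%.
- Any Month 6 diurnal IOP below 6 mmHg therefore meets both the 20% criterion and the 14 mmHg criterion. It stops being a response only if another rule applies, such as explant (SAP section 3) or the second analysis in Protocol 10.4.2.

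**3. Which visits the planned IOP outputs cover**

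Inputs are Protocol 7.2.3, Table 3 in Protocol 7.2.5, and the table shells in SAP section 3.

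- Applanation tonometry is scheduled at 15 of 15 post-implant visits. Eight fall through Month 6: Day 1, Weeks 1 and 2, and Months 1, 2, 3, 4.5 and 6.
- Diurnal IOP after implant is scheduled only at Months 6, 12 and 24, so it covers 1 of those 8 visits.
- The by-subject shell has columns for baseline and Months 3, 6, 12 and 24, so it covers 2 of those 8.
- Neither covers the five visits from Day 1 to Month 2, nor Month 4.5. At 10 planned eyes, the early gap is 5 × 10 = 50 of 8 × 10 = 80 scheduled eye-visits through Month 6.

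**4. What one eye is worth**

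With n = 10, the exact (Clopper–Pearson) 95% limits for x eyes are the 0.025 quantile of Beta(x, n − x + 1) and the 0.975 quantile of Beta(x + 1, n − x). For x = 0 the upper limit is 1 − 0.025^(1/10) = 30.8%.

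| Eyes with low IOP | Rate | Exact 95% CI |
|---|---|---|
| 0/10 | 0% | 0 to 30.8% |
| 1/10 | 10% | 0.3 to 44.5% |
| 2/10 | 20% | 2.5 to 55.6% |
| 3/10 | 30% | 6.7 to 65.2% |

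Under the current wording, each of these rows could sit behind a SAP 4.1 table that shows no hypotony.

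**The case against.** The best defence is that nobody will read safety from one table. Protocol 4.1.1 also evaluates slit lamp and fundus findings through six months. Protocol 10.4.9 promises by-subject listings, and the SAP adds all-visit supportive summaries and individual participant summaries. The adverse event term is introduced as an example, unlisted events can be written in, and Protocol 8.3 requires events to be actively sought at each visit. In ten eyes, low readings can be counted by hand. The study is descriptive, and neither a test nor the halting rule in Protocol 8.7 depends on this rate.

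Most of that stands, and it limits the point. A reader might infer that low pressures would go unseen. The documents do not support that: the readings are collected and may well be displayed. What remains is that nothing requires an isolated low reading to be reported, and no output fixes the threshold, the persistence rule and the denominator together.

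Three other stronger readings also fail.

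- **Severe cases are lost.** Protocol 8.1.1 says "If an adverse event leads to multiple outcomes that sequentially worsen, only the worst adverse event is reported". But hypotony that progresses to maculopathy moves to another listed term in the same by-type table, where it is visible.
- **Missing examinations drive the count.** In Table 3 the column "Month 4.5, 8, 10, 15, 18, &21" has tonometry but no slit lamp or fundus examination. Over 24 months, 6 of 15 visits (40%) lack a slit lamp and 8 of 15 (53%) lack a fundus examination. Through Month 6, the window of the primary summary, the gaps are 1 of 8 and 3 of 8. Protocol 2.3.3 also states that "Subjects will be examined for signs of ocular pathology at each scheduled follow-up visit". Scheduling is a minor contributor.
- **The two counts will probably differ.** Any such probability depends on a per-eye risk that the documents do not give. Their only evidence is preclinical, with no hypotony observed in work involving more than 50 implants.

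**Conclusion.** The concern holds as a gap in prespecified safety reporting. If the listed term is followed as written, the hypotony count can omit eyes that meet the protocol's own numeric definition of a risk it ranks among the most serious. The same reading at Month 6 can count as a response. The gap matters most from Day 1 to Month 2, which neither the by-subject shell nor the diurnal schedule covers.

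Each affected eye is 10 percentage points of a 10-eye denominator. The number affected is unknown and may be zero. The conclusion assumes ten implanted eyes as planned, and that investigators do not routinely write in isolated low readings. If they do, the gap narrows, but the table alone would still not show that they had. The correction is worth making but does not threaten the study's validity.

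**What to change.** Add one table to SAP 4.1, giving n/N with exact 95% CIs:

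- implanted eyes with IOP below 6 mmHg at any post-implant visit;
- implanted eyes with IOP below 6 mmHg at more than 2 visits;
- on a separate line, hypotony with clinical findings.

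Use the applanation value as Protocol 7.1.3.2 defines it: "Two measures are taken from each eye and the average is calculated". Take all implanted eyes as the denominator and include readings up to permanent explant. Make the 6-month window primary and the 24-month window supportive. IOP below 5 mmHg at more than 2 visits, from the guidance in Protocol 7.3.2, can go in a footnote; a full grid of thresholds, persistence rules and windows is more than ten eyes can support.

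The cost is one table from data already scheduled, with no new visit or examination. The low-pressure rate may look less favourable than the adverse event count, and some low readings may have no clinical consequence. The separate line for findings lets the reader judge that.

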8.2 CLASSIFICATION OF AN ADVERSE EVENT

8.2.1 RELATIONSHIP TO DEVICE OR PROCEDURE — CAUSALITY

The relationship between the use of the medical device (including the medical — surgical procedure) and the occurrence of each adverse event shall be assessed and categorized. During causality assessment activity, clinical judgement shall be used and the relevant documents, such as the Investigator's Brochure, the Clinical Protocol or the risk Analysis Report shall be consulted, as all the foreseeable serious adverse events and the potential risks are listed and assessed there. The presence of

confounding factors, such as concomitant medication/treatment, the natural history of the underlying disease, other concurrent illness or risk factors shall also be considered.

Each AE will be classified according to five different levels of causality. The Sponsor and the Investigators will use the following definitions to assess the relationship of the serious adverse event to the investigational medical device or procedures.

- 1) Not related: relationship to the device or procedures can be excluded when:
 - the event is not a known side effect of the product category the device belongs to or of similar devices and procedures;
 - the event has no temporal relationship with the use of the investigational device or the procedures;
 - the event does not follow a known response pattern to the medical device (if the response pattern is previously known) and is biologically implausible;
 - the discontinuation of medical device application or the reduction of the level of activation/exposure when clinically feasible and reintroduction of its use (or increase of the level of activation/exposure), do not impact on the serious event;
 - the event involves a body-site or an organ not expected to be affected by the device or procedure;
 - the event can be attributed to another cause (e.g. an underlying or concurrent illness/ clinical condition, an effect of another device, drug, treatment or other risk factors);
 - the event does not depend on a false result given by the investigational device used for diagnosis, when applicable;
 - harms to the subject are not clearly due to use error;
 - In order to establish the non-relatedness, not all the criteria listed above might be met at the same time, depending on the type of device/procedures and the serious event.
- 2) Unlikely: the relationship with the use of the device seems not relevant and/or the event can be reasonably explained by another cause, but additional information may be obtained.
- 3) Possible: the relationship with the use of the investigational device is weak but cannot be ruled out completely. Alternative causes are also possible (e.g. an underlying or concurrent illness/ clinical condition or/and an effect of another device, drug or treatment). Cases where relatedness cannot be assessed or no information has been obtained should also be classified as possible.

- **4) Probable:** the relationship with the use of the investigational device seems relevant and/or the event cannot reasonably explained by another cause, but additional information may be obtained.
- 5) Causal relationship: the event is associated with the investigational device or with procedures beyond reasonable doubt when:
 - the event is a known side effect of the product category the device belongs to or of similar devices and procedures;
 - the event has a temporal relationship with investigational device use/application or procedures;
 - the event involves a body-site or organ that:
 - the investigational device or procedures are applied to;
 - the investigational device or procedures have an effect on;
 - the serious event follows a known response pattern to the medical device (if the response pattern is previously known);
 - the discontinuation of medical device application (or reduction of the level of activation/exposure) and reintroduction of its use (or increase of the level of activation/exposure), impact on the event (when clinically feasible);
 - other possible causes (e.g. an underlying or concurrent illness/ clinical condition or/and an effect of another device, drug or treatment) have been adequately ruled out;
 - harm to the subject is due to error in use;
 - the event depends on a false result given by the investigational device used for diagnosis, when applicable;
 - In order to establish the relatedness, not all the criteria listed above might be met at the same time, depending on the type of device/procedures and the event.

The Sponsor and linvestigator will distinguish between the serious adverse events related to the investigational device and those related to the procedures (any procedure specific to the clinical investigation). An adverse event can be related both to procedures and the investigational device. Complications of procedures are considered not related if the said procedures would have been applied to the patients also in the absence of investigational device use/application.

Related to Device - Events reasonably anticipated to be related to the physical presence of the device, e.g. erosion, a device deficiency, dislodgment.

Related to Procedure — Events reasonably anticipated to be related to procedures (pertaining to implant) described in this protocol.

NOTE: Procedure related events refers to the procedure related to the initial application of the investigational medical device only and therefore not to any other procedures or treatments applied later throughout the clinical investigation, for instance to treat (serious) adverse events.

In some particular cases the event may be not adequately assessed because information is insufficient or contradictory and/or the data cannot be verified or supplemented. The Ssponsor and the Investigators will make the maximum effort to define and categorize the event and avoid these situations. Where the Sponsor remains uncertain about classifying the serious event, it should not exclude the relatedness and classify the event as "possible".

Particular attention shall be given to the causality evaluation of unanticipated serious adverse (device) events. The occurrence of unanticipated events related to the use of the device (USADE) could suggest that the clinical investigation places subjects at increased risk of harm than was to be expected beforehand.

All AEs will be collected from the time of informed consent through the end of the study. Death should not be recorded as a separate adverse event, but rather as an outcome of the specific SAE which led to the subject's death. Adverse Events that would be reasonably expected to be associated with any surgical procedure (e.g.: anesthesia associated nausea, surgical site pain) will not be categorized as procedure or device related in the 30 days post the surgical procedure.

Notes:

- 1. Any current condition that is recorded as a pre-existing condition is not an AE, unless there is a worsening of that condition in terms of nature, severity, or degree of incidence.
- 2. Technical observations an undesirable device event that does not result in a medically undesirable situation for the subject is not an AE.
- 3. Planned hospitalization for a procedure required by this protocol is not an AE. However, complications during the course of that planned hospitalization that prolong the anticipated duration of the hospitalization do constitute SAEs.
- 4. Elective hospitalization for a pre-existing illness does not constitute an SAE unless the illness has worsened in the nature, severity or degree of the condition with respect to baseline.
- Device dislodgment/expulsion will not be collected as an AE, but rather as a device
 deficiency. If device migration results in a clinical symptom, report this as an AE in addition
 to the device deficiency report documenting device dislodgment/expulsion.
- 6. Lack of efficacy or diminished therapeutic response does not constitute an AE since failure to receive therapeutic benefit is an issue of efficacy, not safety. This includes symptoms that recur in the context of device deficiency leading to loss of therapy.

Removal and/or replacement of the device due to malfunction would be considered a device related adverse event

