8.5 DEVICE DEFICIENCIES

Device deficiencies are defined as inadequacy of an investigational medical device related to its identity, quality, durability, reliability, safety or performance. This may include malfunctions, use error, or inadequacy in the information supplied by the manufacturer.

All suspected investigational device deficiencies should be documented on the appropriate CRF. The Sponsor will investigate all suspected device deficiencies.

Note: a device deficiency can include a device malfunction (i.e.: failure to perform to specifications), and may also include other deficiencies (e.g.: ambiguity of labelling).

For the BGI, not all device deficiencies will lead to an explant. For example, if patency is lost but the device is not causing discomfort, the Investigator and study subject may elect to leave the device in place while implanting a second device or seeking alternative treatment. Thus a device deficiency may not necessarily lead to an AE or SAE. If explanted, a device with a suspected malfunction should be returned to MicroOptx for analysis. If it is not possible to return the device, the reason it could not be returned as well as its final disposition should be documented. Note that reporting of device deficiencies shall be separate from adverse event reporting. If there should be an adverse event associated with the device deficiency, then that adverse event should be reported on an adverse event CRF.

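### Asymptomatic device events can be coded two ways, some early surgical events are barred from relatedness by category, and the main SAP safety table is narrower than the protocol's all-AE endpoint

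*Protocol*

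**What the plan says.** **Device events.** Protocol 8.1.1 defines an AE broadly: "Any untoward medical occurrence, unintended disease or injury or any untoward clinical signs". Protocol 8.1.6 puts a fixed list of terms on the AE form. It includes "Implant migration (of any kind) not requiring surgical intervention", "Implant exposure or extrusion", "Device blockage not requiring surgical revision" and device malfunction, none with a symptom condition. The notes in Protocol 8.2.1 go the other way. The second says "an undesirable device event that does not result in a medically undesirable situation for the subject is not an AE". The fifth says "Device dislodgment/expulsion will not be collected as an AE" and directs the event to a deficiency report, with an AE in addition when migration produces a clinical symptom. Protocol 8.5 allows that "if patency is lost but the device is not causing discomfort" there may be no AE at all, and adds: "Note that reporting of device deficiencies shall be separate from adverse event reporting".

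**Relatedness.** Protocol 8.2.1 requires five-level causality grading of each AE and defines procedure-related events as those reasonably anticipated from the implant procedure. An uncertain serious event defaults to *possible*. The same section says that, for 30 days after surgery, events expected with any operation are not to be classed as procedure or device related. Its examples are nausea from anesthesia and surgical site pain.

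**Scope.** The Protocol Summary and Protocol 4.1.1 make the rate of all AEs through six months the safety endpoint, and 10.4.4 summarizes all AEs. SAP 4.1 limits the primary safety summary to the implanted eye through six months. Its 24-month summaries of device-related events and secondary surgery state no eye limit. SAP 6 adds a listing of all AEs and individual participant summaries.

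**The concern.** The study is meant to show whether the safety profile justifies further work, so AE and device-related AE counts are among its main products. Dislodgment is a listed risk and was seen in preclinical work with earlier device versions, although without clinical sequelae (Protocol 2.3.1 and 2.3.4).

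If two sites can code the same event differently, the AE counts partly reflect coding practice. If early events are barred from relatedness by type, some procedure-related events will be recorded as unrelated, and the halting rule in Protocol 8.7 counts only related serious events. If the main table leaves out systemic and fellow-eye events, the endpoint as defined in the protocol is not a planned output.

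**Working it through.** The plan states no figure to reproduce. The sample size of ten is explicitly not derived (Protocol 10.5). The check is mainly a comparison of texts.

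**(a) Coding.** Protocol 8.1.6 lists 26 terms. Four can name a device event that 8.2.1 or 8.5 treats as a deficiency when there is no clinical consequence:

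- migration without surgical intervention: AE by 8.1.6; not an AE by the second note, or by the fifth note unless symptomatic;
- exposure or extrusion: AE by 8.1.6; expulsion is a deficiency by the fifth note;
- blockage without surgical revision: AE by 8.1.6; by 8.5, lost patency need not lead to an AE;
- device malfunction: AE by 8.1.6; a form of deficiency by 8.5.

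Dislodgment is not a term on the list, but migration of any kind and extrusion cover it. The AE definition does not settle the matter, because an extruding implant can be read as an untoward sign. Symptomatic migration and removal or replacement for malfunction are clearly AEs under 8.2.1. The open case is therefore the asymptomatic event.

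**(b) Relatedness.** The 30-day sentence is defined by type of event and says nothing about seriousness. As a constructed illustration, suppose nausea from anesthesia prolongs the planned stay. The third note in 8.2.1 makes that an SAE. It is reasonably anticipated from the implant procedure, so by definition it is procedure related. The 30-day sentence nevertheless forbids that category. Protocol 8.2.1 also treats complications as unrelated where the procedure would have been done without the device. That does not readily explain the bar, since Protocol 5.2 excludes patients expected to need surgery on the study eye within a year.

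**(c) Scope.** Input: n = 10. Suppose one subject has a systemic SAE by six months that is not device related, and no other SAE occurs.

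- Protocol endpoint: 1/10 = 10%, exact 95% interval 0.3% to 44.5%.
- SAP 4.1 table: 0/10 = 0%, exact 95% interval 0% to 30.8%.

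The intervals are Clopper-Pearson. The upper limit for 0/10 is 1 − 0.025^(1/10) = 0.308, and the lower limit for 1/10 is 1 − 0.975^(1/10) = 0.003.

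**Size of one coding decision.** (x + 1)/10 − x/10 = 1/10, or 10 percentage points. This applies to a type-specific rate. It applies to the any-AE rate only if the subject has no other AE, because a subject already counted leaves that rate unchanged.

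**The case against.** The strongest reply is that nothing is lost. Follow-up forms carry a forced-choice implant-site field and a standardized scale (Protocol 2.3.3). Deficiency and Device Experience forms record the event whatever its AE status. SAP 4.2 tabulates explant by subject, and SAP 4.3 analyzes extrusion as a sign of inflammation, expressly asking whether the sign was raised to an AE. A reader might infer that asymptomatic dislodgments go unrecorded; the documents do not support that. What stands is that no planned table counts these events across both routes.

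On relatedness, a reader might infer that the halting rule is disabled. The text does not support that either. Device-specific events fall outside the 30-day sentence, its examples are minor, and uncertain serious events default to *possible*. The two-monthly safety review and the DSMB act independently of the rule (Protocol 8.7 and 8.8). The default is only a partial safeguard, since it covers uncertainty while the 30-day bar applies even when the cause is clear. How often that would matter cannot be derived from the documents.

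On scope, a reader might infer that systemic and fellow-eye events disappear. They do not. Device-related events and secondary surgery have summaries with no stated eye limit. All AEs are listed, and the enrollment flow diagram reports withdrawals with reasons, which can include death. Death is itself recorded as the outcome of the causative SAE, so it leaves the SAP 4.1 table only if that SAE lies outside the implanted eye. Nor is the narrower 24-month scope a departure: after six months the protocol promises continued follow-up and summaries in update reports, not a rate endpoint.

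It is also fair that the study is descriptive, with ten subjects and by-subject listings. That limits the harm but does not remove the contradictions.

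**Conclusion.** The three inconsistencies are real and modest in size; they should be fixed.

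- Asymptomatic migration, extrusion, blockage and malfunction can be coded as AE or deficiency, so AE counts may depend on the site.
- The 30-day sentence conflicts with the protocol's own causality rules. Its reach into the halting count is narrow and of unknown frequency.
- The SAP 4.1 primary summary is narrower than the protocol endpoint. Systemic and fellow-eye events that are not device related (and are not secondary surgery) appear only in the listing and participant summaries.

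One subject is worth 10 percentage points, under the condition stated above. How many subjects would be affected is unknown.

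The first two conclusions rest on protocol version 9.0 alone. The third compares that version, dated January 2019, with a SAP dated July 2022 and written for Protocol 6054 (formerly 4039). A later protocol version was not supplied and may differ.

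**What to change.** 1. Reconcile Protocol 8.1.6, 8.2.1 with its notes, and 8.5, so that asymptomatic device events are coded one way at all sites.
2. Add a SAP table row counting every migration, dislodgment, extrusion and blockage, whether coded as an AE or as a deficiency.
3. Reconcile the 30-day sentence with the rest of 8.2.1 and with 8.7, so that relatedness of serious events is assessed case by case. A flag for expected surgical events can keep the information the sentence was meant to convey.
4. In SAP 4.1, tabulate all AEs and SAEs through six months, split into implanted eye, fellow eye and systemic.
5. State which protocol version the SAP follows.

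The cost is wording changes, a few table rows and some recoding of completed forms. The reported related-AE rate may rise.
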